2.5.2 Intervention workshop data collection

Subject to consent, we will carry out a short, Likert-style questionnaire at the start and end of the intervention workshop with all workshop participants to capture information on the majority of the secondary outcomes (**Table 2**). The questionnaire will be hosted within a purposely designed REDCap webform and links provided to workshop participants via email at the start and end of the day providing they have consented.

Table 2. Pre- and post-workshop questionnaire

| Statement (please circle your response for each statement) |
|--|
| 1. I have a good understanding of dietary inequalities in my local area 
 • Strongly agree • Agree • Neither agree nor disagree • Disagree • Strongly disagree |
| 2. My organization has a good understanding of dietary inequalities in our area 
 • Strongly agree • Agree • Neither agree nor disagree • Disagree • Strongly disagree |
| 3. I am committed to taking action to reduce dietary inequalities in my local area 
 • Strongly agree • Agree • Neither agree nor disagree • Disagree |

| |
|---|
| 
 • Strongly disagree |
| 
4. My organization is committed to taking action to reduce dietary inequalities in our area
 
 • Strongly agree • Agree • Neither agree nor disagree • Disagree • Strongly disagree |
| 
5. I am confident that I can contribute to reducing dietary inequalities in my area
 
 • Strongly agree • Agree • Neither agree nor disagree • Disagree • Strongly disagree |
| 
6. I am confident that my organization can contribute to reducing dietary inequalities in our area
 
 • Strongly agree • Agree • Neither agree nor disagree • Disagree • Strongly disagree |
| 
7. There will be meaningful collaboration between local partners to reduce dietary inequalities in our area over the next 12 months
 
 • Strongly agree • Agree • Neither agree nor disagree • Disagree • Strongly disagree |
| 
8. I am comfortable working with 'complex' or 'wicked' problems (these are problems that require intersectoral collaboration and not just more time and more money)
 
 • Strongly agree • Agree • Neither agree nor disagree • Disagree • Strongly disagree |
| 
Please provide your details
 
 • What is your role within your organisation? |

- How long have you been in this role?
- How long have you been in a role relevant to dietary inequalities?

2.5.3 Consent

Electronic informed consent (EIC) will be collected for each LAKI ahead of baseline data collection and workshop participants at the start of each intervention workshop. All EIC will be collected in a study specific Research Electronic Data Capture (REDCap) webforms. This secure, GDPR-compliant platform will guide participants through the consent process step-by-step, ensuring they understand the study and their participation. The form will include detailed information about the study's aims, procedures, data confidentiality measures, and the voluntary nature of participation (outlined in a relevant participant information sheet). Participants will have the opportunity to discuss any questions or concerns with the research team before completing the e-consent process. All EIC responses will be stored within the IMS Epidemiology Unit's Secure Research Domain (SRD).

2.5.4 Intervention cost data collection

The mean cost of the intervention will be calculated based on time, travel and accommodation costs to the research team; time and hosting costs to LAs; and time costs to workshop participants. The study team will keep notes of their costs for each workshop held and estimate costs to LAs based on seniority of LAKIs and venues used, and costs to workshop participants based on seniority and organisation.

2.6 Intervention

As we deliver the intervention outlined above in section 1.2, we expect to make modifications to further refine it. Given the intervention is entirely researcher delivered, we don't expect participant-led deviations from protocol, nevertheless we will conduct an intention to treat analysis. To monitor changes or adaptations to the intervention and ensure the intervention is being delivered with fidelity, we will use the Framework for Reporting Adaptations and Modifications-Enhanced (FRAME). (14) This framework will allow us to track the kinds of changes being made to the intervention and the purpose of the changes. Changes made will be recorded in a spreadsheet modeled after this framework.

2.7 Participant timeline

We expect each LAKI in the intervention arm to be required to commit approximately 2 days over the course of approximately 12 months to the study for both data collection and intervention. Those in the control arm will be required to commit around 2 hours over ~12 months for data collection only. For workshop participants (stakeholders recruited by the LA), time commitment will be one day for the workshop. LAKI and workshop participants may also be invited to take part in interviews for the qualitative process evaluation as described below. We anticipate starting the recruitment process in April 2026 with data collection completed by June 2028.

2.8 Qualitative Process Evaluation Methodology

2.8.1 Process Evaluation Background

Our qualitative process evaluation (PE) involves the study of implementation, mechanisms and context and can help understand why intervention effects occurred (or did not). (15) Our secondary quantitative outcomes also include potential mechanisms. The exploratory quantitative analysis will assess differential effects based on context. In addition to these quantitative components, the PE will also include qualitative observations and interviews. This aspect of the PE will adopt a realist- and systems-informed approach, guided by the MRC framework for process evaluation of complex interventions (15, 16) and aligned with systems-oriented perspectives such as ENCOMPASS. (17)

2.8.2 Aims and Objectives of the qualitative aspect of the Process Evaluation

To understand how the GMB workshops are implemented, experienced, and interpreted by participants, and identify mechanisms through which they may (or may not) lead to changes (intended/ unintended) in local food systems addressing DHI.

Objectives:

1. **Implementation Fidelity:** Assess how GMB is delivered across LAs, the extent to which delivery aligns with the protocol, what adaptations occur and why;
2. **Context:** Examine how local, regional, and national contexts shape the framing of DHI, barriers/enablers to solution development, and patterns of engagement;
3. **Mechanisms of Change:** How participants interpret, respond, and act on the intervention, including mechanisms theorised in the 'theory of change' logic model e.g. developing shared understandings, commitment, collaboration and confidence.
4. **Evolution of Understanding:** Track how stakeholder understandings evolve during and after GMB, and compare this to the control arm;
5. **Outcome Linkage:** Assess whether and how GMB influences the type and prioritisation of solutions proposed, and the extent to which these are implemented locally. This is to complement the RCT's quantitative outcome data and to support with interpretation rather than assess effectiveness.

2.8.3 Methods

Overview and sample

The qualitative PE will use a qualitative mixed-methods, embedded design. Data collection will occur in approximately 20 purposively sampled local authorities (~10 intervention, ~10 control), representing diverse geographies, organisational structures, and socio-demographic profiles. Within each LA, we will work with the key informants to identify people to interview (intervention and control) based on their role, knowledge, and involvement in DHI-relevant activities and suitable workshops/meetings to observe (control LAs only).

In each of the ~10 intervention PE sites activities will include:

- Intervention workshop **observations**
- post workshop **semi-structured interviews** with the key informant and one other workshop attendee
- 6-12 month post workshop follow-up semi-structured interviews with the same two participants (i.e key informant and one other meeting attendee)

In each of the ~10 control PE sites, we will identify and recruit interview participants in collaboration with the LAKI and work with them to select and negotiate access to relevant team meetings or planning events they are involved in that could serve as a comparable control to the intervention workshops. This will include gatherings like holiday hunger working group meetings, food programme meetings, and food poverty action plan workshops. We will then observe these meetings / events and interview around two attendees (LAKI plus one other) using the same data collection tools and approaches as we are using for the intervention workshops, so that they can be compared. This will help us distinguish between features, outcomes and perceived effects that are either (i) inherent to some collaborative team-based approaches to addressing dietary health inequalities or (ii) particular to the intervention workshop.

Workshop observations

Intervention LAs (≈10) and Control LAs (≈10):

- Structured observations of intervention workshops using a semi-structured pro forma.
- Unstructured fieldnotes documenting emerging reflections, unexpected observations, and contextual insights.

Observations will explore issues such as how DHI are characterised and framed, how lived experienced and other local contextual factors are taken into account, the types and reach of proposed solutions, consideration given to different types of evidence, how different individuals and sectors contribute, and conflict and consensus. Alongside unstructured fieldnotes, we will use a semi-structured observation pro-forma, drawing on principles of organisational ethnography.

Post observation semi-structured interviews

Interviews with two participants (LAKI plus one other) from each of the 10 control LAs and the 10 intervention LAs (a total of ≈ 40 participants)

- Interviews to be conducted with individuals (who will have attended the intervention workshop or comparable control event) within one week of the observation.
- Follow-up paired interviews with these same individuals 6 to 12 months after the initial interview.

Semi-structured interviews will explore participants' understandings of DHI, and potential solutions, and how these evolve. Two individuals will be interviewed from each LA either as a pair or separately, depending on their preference, either online or in person. Follow-up interviews will explore any changes in perception, understanding, working practices, collaborations, and approaches around dietary health inequalities. Interviews will be audio-recorded (with consent), transcribed and pseudonymised according to job title.

3 Statistical Considerations

3.1 Sample Size for quantitative analyses

We will recruit 60 LAs: 30 each in the intervention and control arms. We will recruit one key informant per LA (n=60). We aim to recruit all workshop participants (n≈450). Given novelty, we do not have robust data to inform sample size calculations. Instead, we used best practice guidance on pilot studies suggesting ~25-35 per arm to

detect small effect sizes with 90% power. (18) A sample size of 60 has 72% power to detect a difference of two policies if the standard deviation is 3, and 97% if it is 2.

We will use baseline data to re-estimate the sample size required to detect a difference of two policies with 90% power. (19) If this is ≤ 60 , we will consider the study adequately powered. If it is >60 , we will consider it underpowered and disseminate as a pilot study. Our data will be made available for others (or us) to add to in the future.

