| Key Inclusion/Exclusion Criteria | All Local Authorities (LAs) in England will be eligible to participate. However, we will start recruitment by targeting the 40% most deprived LAs in England. Local authority Key Informants (LAKI) will be eligible if they (a) work at participating LA, and (b) have a core responsibility for food policies. Workshop participants will be eligible if they are attending the intervention workshop and happy to provide consent for participation. |
| Study Type | A single centred, unblinded, parallel-group superiority RCT |

| | |
|-------------------------|--|
| Target Sample Size | 60 LAs, 30 per group |
| Primary Outcome | Number of policies planned or implemented within the last 12 months that explicitly aim to reduce dietary health inequalities (DHI) |
| Key Secondary Outcomes | 
 • Distribution of polices across a scale of potential to achieve system change (Potential of policies) • Perceptions of: 
 ○ Personal and shared local understanding of DHI (Understanding) ○ Personal and shared commitment to address DHI locally (Commitment) ○ Strength of local collaborations to address DHI (Collaboration) ○ Confidence that additional solutions to address DHI locally will be implemented in the next 12 months (Confidence) |
| Intervention duration | 1 workshop plus around 3 pre-meets and 1 post-meet |
| Follow up duration | 12 months |
| Date of first enrolment | TBC |
| Planned Study duration | Three years |

Protocol Signatures

I agree to ensure that the confidential information contained in this document will not be used for any other purpose beyond the evaluation or conduct of the investigation with the prior written consent of the Sponsor.

I also confirm that I will make the findings of the study publicly available through publication or other dissemination tools without any unnecessary delay and that an honest, accurate and transparent account of the study will be given; and that any discrepancies from the study as planned in this protocol will be explained.

Chief Investigator: [name]

Signature:

Date: 02 Feb 2026

Protocol Revision Chronology

| Version | Date | Details |
|---------|------------------|-------------------|
| 1.0 | 02 February 2026 | Original protocol |

Contents

| | |
|---|----|
| List of Abbreviations..... | 6 |
| Trial flow chart/other figures | 7 |
| 1 Introduction | 9 |
| 1.1 Background and rationale | 9 |
| 1.2 The Intervention | 9 |

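### The sample-size rationale says about 25-35 per arm detects small effects with 90% power; the protocol's own next sentence contradicts this, and 30 per arm gives about 12% unadjusted power for a standardised difference of 0.2.

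*Protocol*

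**What the plan says.** Section 3.1 sets the size: "We will recruit 60 LAs: 30 each in the intervention and control arms". It says that novelty leaves no robust data for a formal calculation, and gives a basis in its place that opens with "we used best practice guidance on pilot studies suggesting ~25-35 per arm to". The rest of that sentence, and the start of the one after it, read: "detect small effect sizes with 90% power. (18) A sample size of 60 has 72% power to detect a difference of two policies". The number in the bracket is a citation to a review of pilot and feasibility sample sizes.

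The second sentence concerns the trial's own target. Its 72% is for an SD of 3; for an SD of 2 the protocol puts the power at 97%.

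The following paragraph plans to use baseline data to "re-estimate the sample size required to detect a difference of two policies with 90% power". If more than 60 LAs are needed, the study will be regarded as underpowered and reported as a pilot.

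Section 3.3 makes the main analysis a linear regression adjusted for baseline. The protocol does not define a small effect, and gives no significance level, sidedness, baseline to follow-up correlation or allowance for loss to follow-up.

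**The concern.** The clause on small effects is the only reason given for choosing about 30 per arm, and it attaches a power to that size. The sentence after it attaches a lower power to a much larger effect at the same size. Both cannot describe one two-arm comparison. What is at stake is the sensitivity that the protocol claims for itself: as written, the trial appears able to find small effects reliably, when it would usually miss them.

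**Working it through.** **Inputs.** From section 3.1: 30 per arm; range 25-35 per arm; difference 2 policies; SD 3 or 2; 90% power claimed for small effects. From section 2.1: 1:1 allocation. Assumed: two-sided 5%, all 60 LAs analysed, and 0.2 as a conventional value for small.

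**Formula.** With n per arm and standardised difference d = difference / SD, the noncentrality is d × √(n/2). Power is approximately Φ(d√(n/2) − 1.960). The exact figures use the noncentral t distribution with 2n − 2 degrees of freedom.

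**Step 1: reproduce the protocol's figures (n = 30, √15 = 3.873).**
- SD 3: d = 2/3 = 0.667; 0.667 × 3.873 = 2.582; Φ(0.622) = 0.733; exact 0.719. Stated: 72%.
- SD 2: d = 2/2 = 1.0; Φ(3.873 − 1.960) = Φ(1.913) = 0.972; exact 0.968. Stated: 97%.

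Both reproduce. A one-sided 5% test gives 0.82-0.83 for SD 3, which does not match 72%, so two-sided 5% is the natural reading.

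**Step 2: the contradiction, without defining small.** For a fixed size and test, power falls as the effect shrinks. Power is 72% at d = 0.67, so it is below 72% at every smaller d. Using 35 per arm does not help: exact power at d = 0.67 is then 0.785, still below 90%.

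**Step 3: power for small effects (exact, unadjusted).**

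| d | 25 per arm | 30 per arm | 35 per arm |
|---|---|---|---|
| 0.2 | 0.107 | 0.119 | 0.131 |
| 0.3 | 0.180 | 0.208 | 0.236 |
| 0.5 | 0.410 | 0.478 | 0.541 |

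**Step 4: what 90% power does detect (unadjusted).** Approximately d = (1.960 + 1.282) × √(2/30) = 3.242 × 0.258 = 0.84; exact 0.85 (0.94 at 25 per arm, 0.79 at 35). In policies, 2 / 0.851 gives an SD of about 2.35 or less. For d = 0.2, 90% power would need about 527 per arm.

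**Step 5: effect of baseline adjustment.** With baseline to follow-up correlation r, the residual SD is SD × √(1 − r²). The detectable d is then about 0.851 × √(1 − r²), and the largest SD for two policies is 2 divided by that. The values of r are assumed.

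| r | √(1 − r²) | power at d = 0.2 | d for 90% power | largest SD for two policies |
|---|---|---|---|---|
| 0 | 1.000 | 12% | 0.85 | 2.35 |
| 0.3 | 0.954 | 13% | 0.81 | 2.46 |
| 0.5 | 0.866 | 14% | 0.74 | 2.71 |
| 0.7 | 0.714 | 19% | 0.61 | 3.29 |
| 0.9 | 0.436 | 42% | 0.37 | 5.39 |

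Even r = 0.97 gives only about 88% at d = 0.2.

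**The case against.** Four arguments can be made for the plan.

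*The clause reports outside guidance, not this trial's power.* The cited review is not available here, so what its 90% refers to cannot be checked; it may not be this comparison at all. That stands as a caution about the source. It does not save the sentence, which ties the 90% to 25-35 per arm and uses it to support 60 LAs.

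*The main analysis adjusts for baseline.* This matters for the detectable difference. At r = 0.7, power for two policies with SD 3 rises to about 94%, so the SD limit of 2.35 holds only without adjustment and must be labelled so. For the same reason it would be too absolute to say that no two-arm comparison of this size could detect a small effect: a correlation a little above 0.97 would reach 90% at d = 0.2. Nothing in the protocol suggests a correlation that high.

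*No decision depends on the clause.* This is correct. The adequacy rule concerns two policies at 90% power, not small effects, and a requirement above 60 leads to reporting as a pilot.

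*Readers would not be misled.* A reader might infer that the 90% rule is presented as already met, or that a null result would be taken to rule out small effects. The documents support neither. The 72% figure stands next to the clause, the question is left open until baseline data arrive, and the only interpretive rule provides for calling the study underpowered.

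**Conclusion.** The concern holds as an internal contradiction in section 3.1. Step 2 needs no definition of small and no access to the citation; it needs only that both sentences refer to the same two-arm comparison. The size of the discrepancy does rest on assumptions: with two-sided 5% and small taken as 0.2, the claimed 90% is about 12% unadjusted at 30 per arm, and 14-19% with baseline adjustment at r = 0.5 to 0.7.

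A reader might go further and infer that the trial's power calculations are wrong or that 60 LAs must be increased. The documents do not support that. The 72% and 97% figures are correct for 60 analysed LAs without adjustment, and the re-estimation and pilot rule limits the practical harm. What is wrong is a stated power on which the choice of size rests.

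**What to change.** In section 3.1, delete the clause on small effects, or state correctly what the 90% in the cited pilot guidance refers to, without presenting it as this trial's power. Put in its place:

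*60 analysed LAs (30 per arm) give 90% power, two-sided 5%, unadjusted for baseline, for a standardised difference of about 0.85, i.e. two policies if the SD is about 2.35 or less. Baseline adjustment lowers the detectable difference depending on the correlation (about 0.74 at r = 0.5 and 0.61 at r = 0.7, assumed values). The trial is not powered for small effects.*

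Keep the 72% and 97% sentence, labelled as unadjusted and for 60 LAs with 12-month data.

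The cost is protocol wording only. The number of LAs, the main analysis and the re-estimation rule are unchanged. The one downside is that the stated sensitivity becomes less favourable.

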3.2 Randomisation & Enrolment

Trial LAs will be unblinded (open label) and randomised using a computer-generated randomization list with a 1:1 ratio. Specifically, our study statistician will generate the randomisation list using Stata statistical software. Stata makes use of a computer system clock as the seed point, which produces a pseudo-random list generally regarded as acceptable for RCTs.

3.3 Analysis Plan

The main analysis will use linear regression to compare the mean number of policies between intervention and control groups, adjusted for baseline. It will include all LAs in the group they were randomized to (i.e., intention-to-treat). We will similarly assess changes in potential of policies to achieve system change, and Understanding, Commitment, Collaboration and Confidence in an RCT framework in LA key informants at baseline and 12 months; and in a pre-post framework in all workshop participants at the start and end of workshops. Exploratory interaction and sub-group analyses will assess if the intervention is differentially effective in LAs based on differentiating characteristics between LAs (for example those in HDRC partnerships or those with food strategies) to gain insight to DHI-focused policy implementation and understand better any potential limitations to generalizability.

Qualitative data will be managed and thematically analysed (Thorne S 2000) using NVivo, following an iterative, interpretive coding process:

- Open coding (informed by Theory of Change (**Figure 1**)): initial identification of key ideas, actions, participant responses, mechanisms, and contextual influences emerging from the data.
- Axial coding: Organisation and refinement of codes into broader analytic categories e.g. implementation fidelity, mechanisms of change, contextual influences, and the evolution of understandings and practices over time.
- Integrative analysis (selective coding): development of an integrated explanatory account, informed by realist principles, which explores how mechanisms operate under different contextual conditions and how this varies between GMB and control settings.

Analytic credibility will be supported through triangulation across observations, interviews, and documentary sources, and through comparative analysis of GMB and control settings with attention to contextual variation and emergent processes. Where appropriate, qualitative findings will be used to aid interpretation of quantitative outcome measures. In order to provide context for the data collection and analysis we will scope relevant documents including:

- workshop agendas, scripts, attendance lists, CLDs and other workshop outputs

- LA food strategy documents, policy submissions
- Food Foundation DHI data

4 Data Management

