1.3 Research Questions

1) What is the impact of the intervention on the primary and secondary outcomes listed below?

2) How do local stakeholders understand DHI and their potential solutions, how does this evolve during the course of the intervention?

3) What are the costs of the intervention?

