1.4.2 Secondary outcomes

- Distribution of policies across a scale of potential to achieve system change (Potential of policies)
- Perceptions of:
 - Personal and shared local understanding of DHI (Understanding)
 - Personal and shared commitment to address DHI locally (Commitment)
 - Strength of local collaborations to address DHI (Collaboration)
 - Confidence that additional solutions to address DHI locally will be implemented in the next 12 months (Confidence)

2 Methods

This protocol presents the quantitative data collection methodology led by the University of Cambridge, followed by the qualitative process evaluation methodology led by the University of Hertfordshire (Section 2.8)

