2.5 Randomised Control Trial Data collection

2.5.1 Local authority level baseline and 12-month data collection for primary outcome

Based on the logic model described in Figure 2, data will be collected from each LA on the primary outcome at baseline and 12 months to document existing policies related to dietary inequalities prior to randomisation and intervention implementation. These data provide a reference point for assessing change at the 12-month follow-up interview. A structured interview guide will be used with a checklist of questions (**Table 1**) to identify policies. All interviews will be recorded on Microsoft Teams. Interviews will be conducted by a member of the research team with the LAKI. The interview recording and generated transcription will be stored until the data capture form has been completed and will then be deleted.

Table 1. Key Informant interview guide for baseline data collection

| Variable | Interview guide |
|----------------------------------|--|
| Date | 1. Date of data collection |
| LA and KI information | 
 1. Name of LA 2. What role does the Key Informant have 3. How long as the Key informant been in their current role? 4. How long has the Key Informant been in a role relevant to dietary inequalities |
| Current food strategies | 
 1. Does the LA have a current Food Strategy (Y/N) 2. Is the LA part of a local food partnership (Y/N) 3. Is the LA a member of the Health Determinants Research Collaboration (Y/N) |
| Current policies for DHI (known) | 1. Can you tell me what policies have been put in place in the last 12 months or will be put in place in the next 12 months to address dietary inequalities (defined as any intentional actions explicitly aiming to address dietary inequalities)? Use relevant prompts with examples from the Food System Transformation Solution Bank |

| | |
|--|---|
| | 
 2. For each policy: what was (or will be) the date of implementation? 3. For each policy: please tell me more about that, what it involves etc Is there anything else that's relevant for this policy? (for each response on a particular policy, ask again about details and repeat until data saturation is achieved for that policy). 4. Are there any other policies in place to address dietary inequalities? Repeat the above questions (i.e., 2-4) for each policy until all policies known to the Key Informant are given. |
|--|---|

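### Section 3.3 plans a randomised comparison of four secondary outcomes in key informants, but the data-collection sections describe no instrument that would supply the scores

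*Protocol*

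**What the plan says.** Research question 1 (Section 1.3) asks "What is the impact of the intervention on the primary and secondary outcomes listed below". Section 1.4.2 lists five secondary outcomes: the potential of policies to achieve system change, and four perceptions (Understanding, Commitment, Collaboration and Confidence).

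Section 3.3 gives the perceptions two analyses. One is randomised: "Understanding, Commitment, Collaboration and Confidence in an RCT framework in LA key informants at baseline and 12 months". It is introduced as similar to the main analysis, a linear regression between arms adjusted for baseline. The other is not randomised: "in a pre-post framework in all workshop participants at the start and end of workshops".

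On collection, Section 2.5.1 states that "data will be collected from each LA on the primary outcome at baseline and 12 months", with the baseline part taken before randomisation. "A structured interview guide will be used with a checklist of questions", and its stated purpose is to identify policies. The guide is headed "Table 1. Key Informant interview guide for baseline data collection". Section 2.5.2 describes a "short, Likert-style questionnaire at the start and end of the intervention workshop with all workshop participants" (Table 2) and presents it as the source for most of the secondary outcomes. Section 2.4 places the workshops in the intervention LAs.

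**The concern.** The analysis section and the data-collection sections do not fit together. The first needs a score for each key informant, in both arms, at two times. The second describes perception scores from a different group of people, in one arm, at two times on a single day.

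At stake is the randomised evidence on most of the secondary outcomes, which Section 2.8.1 says include potential mechanisms of the intervention. The trial is open label and the perceptions are self-reported. A change between the morning and the evening of a workshop, with no comparison group, cannot by itself answer a question about impact. A statistical analysis plan cannot close this gap, because it can only analyse data that someone has been told to collect.

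**Working it through.** The point rests on matching the planned analysis to the described instruments. The arithmetic is a count.

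**What the randomised analysis in 3.3 needs.** Scores on four perceptions from one key informant in each of 60 LAs (30 per arm, Section 3.1), at baseline and at 12 months.

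**What each described source gives.**

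| Source | Who | When | Perception scores? |
|---|---|---|---|
| Key informant interview, Table 1 (2.5.1) | Key informants, both arms | Baseline and 12 months; guide titled for baseline | None. Items cover the date, LA and informant details, food strategy, partnership and research-collaboration membership, and policies |
| Questionnaire, Table 2 (2.5.2) | Workshop participants, intervention LAs only | Start and end of the workshop day | Yes, eight Likert items |
| Process evaluation interviews (2.8.3) | Two people in each of about 10 intervention and 10 control LAs | Within a week of an observed event, and 6 to 12 months after that | No, qualitative |

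**Count for the planned comparison.**
- Control key informants with a score: 0 of 30 at baseline and 0 of 30 at 12 months.
- Intervention key informants with a score: 0 of 30 at baseline and 0 of 30 at 12 months. One who attends the workshop would complete Table 2 on that day, which is neither time point.
- Outcomes affected: 4 of 5. The fifth, potential of policies, concerns the policies that the interview records.
- Quantitative perception data that would exist: about 30 × 15 = 450 workshop participants, all in the intervention arm.

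**Does Table 2 cover the four outcomes?** Items 1–2 address Understanding, 3–4 Commitment, 5–6 Confidence and 7 Collaboration. Section 1.4.2 defines Confidence as belief that further local solutions will be put in place in the coming 12 months. Items 5–6 ask instead whether the respondent, or their organisation, is able to contribute. The form therefore does not measure Confidence as defined.

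**Context: what 30 per arm could show if the data were collected.** The protocol's power figures are for the primary outcome. Assuming a two-sided 5% level (Section 3.1 states none), a two-sample t-test with 30 per arm and a difference of two policies gives 71.9% power at SD 3 and 96.8% at SD 2, which agrees with the stated 72% and 97%. On the same assumption, the effect detectable with 80% power and no baseline adjustment is close to (1.960 + 0.842) × √(2/30) = 0.72 SD by the normal approximation, and 0.74 SD by the exact t calculation. The finding does not depend on this figure.

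**The case against.** The best defence is that Section 3.3 itself shows an intention to measure key informants in both arms. Section 2.5.1 is headed as being for the primary outcome, so secondary items would not be expected there. Table 1 is titled for baseline and no 12-month guide is shown. Section 2.7 allots control informants about two hours for data collection without itemising it. A reader might therefore infer too much in saying that control informants will never be asked. That stands: the documents show that no such collection is described, not that none will happen. The mismatch remains, because staff working from Sections 2.5.1 and 2.5.2 would not collect these scores.

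A reader might also infer that only the same-day workshop change would be left. The documents do not support that. Section 2.8.2 sets out to follow how understanding evolves and to compare it with the control arm, and Section 2.8.3 plans repeat interviews in about 10 control LAs. These interviews are unscored, cover about a third of the LAs and are timed around an observed event. Section 2.8.2 says that they support interpretation and do not assess effectiveness. They cannot supply the regression.

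A third tempting reading is that the loss becomes irreparable once baseline interviews start. It does not. Under randomisation, a comparison between arms at 12 months is valid without baseline values, and baseline adjustment mainly adds precision. What would be lost for LAs already interviewed is the adjustment and any change from baseline.

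**Conclusion.** The point holds as a contradiction between Section 3.3 and Sections 2.5.1–2.5.2. As described, 4 of 5 secondary outcomes have no quantitative control-arm data and no key-informant scores at baseline or 12 months, so the baseline-adjusted randomised comparison cannot be carried out. This rests on reading Section 2.5.1 as setting the scope of collection at both times. For baseline, Table 1 confirms that reading directly. For 12 months it rests on the text alone, since no separate guide is shown.

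The primary outcome, its analysis, the randomisation and the sample size are unaffected. The matter should be settled before the first baseline interview, because that is the only time at which the analysis planned in Section 3.3 can be secured in full.

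**What to change.** - In Section 2.5.1, add the Table 2 items for all 60 key informants in both arms, completed at baseline before randomisation and again at 12 months. Carry this into the interview guide, and supply or reference a 12-month version.
- Add or reword an item so that Confidence is measured as Section 1.4.2 defines it. The form should not be reused unchanged.
- In Section 3.3, keep the baseline-adjusted comparison in key informants as the analysis of effect for these four outcomes, and label the workshop pre-post change as supportive and uncontrolled.
- If the items are not added, remove the randomised comparison of these four outcomes from Section 3.3 and align research question 1 with what remains.

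The cost is a protocol edit and one short existing REDCap form, adjusted and sent twice to 60 people, or 60 × 2 = 120 completions. It should fit within the roughly two hours already allotted to control informants. The key informant information sheet, consent form (Section 2.5.3) and ethics approval (Section 6) must be checked for cover of the questionnaire. If they do not cover it, they need amending too. Recruitment is expected to start in April 2026, which sets the timetable.
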